5 STUDY DEVICE

5.1 Description

Epidural spinal cord stimulator (Model 3086, Model 3874, Abbott Neuromodulation; Nomad, Ripple Neuro)

The ES electrode lead is an implantable neurostimulation device that is FDA-approved for treatment of neuropathic pain disorders. ES leads will be implanted temporarily along the dorsal epidural surface of the lumbosacral enlargement (i.e., L2-S1 spinal segments). The externalized ends of the ES electrode leads will be connected to the Nomad neurostimulation system in order to deliver testing-specific electrical pulse waveforms to the epidural surface (Figure 4). ES pulses will be synchronized to electrophysiological and biomechanical recordings of spinal motor output, and in turn, motor functions that are enabled by ES. Electrophysiological data will be collected from skin surface electrodes. Additionally, during ES using the Ripple Nomad, signals will also be captured from passive electrodes (i.e., not configured as an anode or cathode during stimulation) on the ES lead (Abbott, Model 3086). During ES-enabled rehabilitation sessions, when non-testing-specific electrical pulse waveforms are applied, the Abbott clinician programmer device designated for the ES leads will be used.

Transcutaneous spinal cord stimulator (DS8R, Digitimer LLC)

The DS8R is designed for human research rather than diagnosis or therapy; it does not have a medical device certification. The DS8R is an isolated, constant current stimulator for human research studies involving nerve and muscle stimulation via surface electrodes. It features a high compliance voltage and can be triggered and controlled by multiple external sources. For the purpose of delivering TS to the surface of the skin over the spine, customized electrical waveforms built within Labchart electrophysiological data acquisition software (ADInstruments Inc., Colorado). The DS8R will be triggered to deliver TS waveforms via PowerLab digital outputs (ADIstruments Inc., Colorado). The DS8R is capable of delivering monophasic or biphasic current pulses of up to 2ms duration, with an output range of 2mA to 1000mA* (from 400V). The actual current achieved will be restricted by a pulse energy limit of 300mJ per pulse and the skin/electrode resistance.

5.2 Method for Assigning Subjects to Treatment Groups

Four subjects will be assigned to each treatment arm based on availability at the time the subject volunteers to participate (Total subjects studied: 8). If both arms are enrolling in

parallel at the time a subject volunteers to participate, he/she will be allowed to choose the treatment arm in which to enroll.

5.3 Preparation and Administration/Implantation of Investigational Device

Description of TS administration

[figure not shown]
A constant-current stimulator DS8R (Digitimer LLC) will be used to deliver TS to the skin surface over the spine. At locations where self-adhesive bipolar recording electrodes will be placed onto the skin, the area will be cleaned with alcohol to ensure secure attachment and enhance signal recordings. The stimulation will be administered using self-adhesive electrodes placed as cathodes on the skin between the T7 and L3 vertebrae, with the option of ultrasound (US) guided imaging to locate the spinous processes at each segment. In addition, self-adhesive electrodes will be placed symmetrically on the skin serving as anodes. A foam pad may be placed over the cathode and secured using adhesive tape and/or an elastic belt to tightly wrap around the subject's trunk to ensure cathode electrodes do not shift or peel away during rehabilitation activities. The stimulation waveform will consist or bi-phasic pulses (duration between 0.1 - 1.0 ms), at frequencies between 0.2 - 100Hz. We will also test the efficacy of a recently developed carrier frequency of 4 - 10 kHz, using stimulation intensities of up to 100 mA. Skin under the electrodes will be inspected frequently during sessions to ensure no irritation occurs from stimulation.

Description of ES system implantation/administration

We recently published a detailed explanation of the procedure to implant a permanent electrode array connected to an implanted pulse generator, along with a detailed description of the electrophysiological approach used to guide electrode positioning over the lumbosacral enlargement in humans with SCI (Calvert, 2018). The same approach will be used during this study to guide electrode placement via electrophysiological monitoring of spinal motor evoked potentials.

The procedures for percutaneously implanting Abbott ES electrodes are performed daily at Mayo Clinic to treat patients suffering from neuropathic pain. Prior to implantation, subjects will undergo a pre-operative evaluation to minimize the risk of unexpected complications. Pre-operative assessments may be performed to check for any signs of infection.

In order to implant the temporary spinal electrodes, an incision will be made at the entry site to the depth of the subcutaneous fascia. Under fluoroscopy, an electrode insertion needle will be place into the epidural space using a paramedial approach until resistance is felt from the ligamentum flavum, followed by fluoroscopic visualization of the needle's position. Once positioning is confirmed, the needle stylet will be removed and the needle will be advanced into the epidural space.

Then, the leads are advanced in an anterograde fashion to deliver them into the intervertebral foramen under fluoroscopic guidance. Following electrophysiologic confirmation of electrode positioning, the needle and stylet will be removed, the implantation site will be dressed, and the leads will be secured to the skin via an adhesive bandage. The implantation site will be monitored for signs of infection, tissue erosion, or dislodged lead wires.

Procedure to explant ES electrode leads

After completing 12 sessions of rehabilitation with ES, the adhesive bandage covering the implantation site will be removed, the incision site will be opened, and the leads will be carefully retracted. Finally, the incision site will be cleaned and dressed.

If complications associated with temporary lead implantation (e.g., infection, severe lead migration, device malfunction, etc.) are observed, the PI will make an informed decision whether to perform explantation prior to completion of 12 rehabilitation sessions.

5.4 Subject Compliance Monitoring

Throughout the study, research staff will monitor study protocol compliance. This will include review and verification of all protocol-related procedures and records. The PI will oversee compliance and determine the appropriate response to non-compliance events.

5.5 Prior and Concomitant Therapy

A subject's prior therapy regimen will not impact the PI's decision regarding enrollment into the study. As long as the subject fits the inclusion criteria and does not demonstrate any exclusion criteria characteristics (i.e., bone fractures, joint contractures, or skin lesions), prior exercise or therapy programs will not exclude their participation in the study. While enrolled in the study, subjects will be asked to follow the instructions from the study staff regarding the home exercise program prescribed from the research team. For example, if the study subject performed locomotor training at a local gym prior to the study, they would be asked to discontinue that activity while participating in the trial.

5.6 Packaging and Labeling

The packaging of the devices will be from the manufacturer's clinical supply. The following will be added to the devices used within this investigation:

"CAUTION – Investigational Device. Limited by Federal (or United States) law to investigational use"

5.7 Masking/Blinding of Study

This is an unblinded study. The PIs, co-investigators, and subjects will know what treatment they received.

5.8 Receiving, Storage, Distribution and Return

5.8.1 Receipt of Investigational Devices

The ART laboratory owns two transcutaneous electrical spinal stimulators (DS8R Isolated Biphasic Constant Current Electrical Stimulator, Digitimer Ltd), which serve as a primary unit and a reserve unit. If either device becomes damaged or unusable, use of the device will be discontinued until the supplier repairs the unit. All communication between study staff and the supplier will be documented in the study files.

A representative from Abbott will ship the devices to Mayo Clinic and they will be properly inventoried prior to the scheduled date of surgical implantation. The representative will also train study personnel on how to use the clinician programmer during non-testing rehabilitation sessions.

The Nomad neurostimulation system will be purchased from Ripple Neuro, shipped to Mayo Clinic, and inventoried within the ART Lab.

Any product discrepancies or damage will be documented in the study files and the supplier will be notified. Then, appropriate action will be taken by the PI to fully address the issue.

5.8.2 Storage

The TS device (Digitimer) is stored in the ART laboratory, a secured area requiring badge access.

ES electrode leads will be stored within a secured surgical materials area of Mayo Clinic's Pain Clinic. Access to this area is granted solely to Mayo Clinic staff involved in surgical implantation procedures.

The Ripple Nomad system will be stored in the ART Lab, which is a secured area that can only be accessed by ART Lab staff.

5.8.3 Distribution of Study Device

The TS devices (Digitimer) will not be assigned to individual subjects, but the devices on hand will be tracked in the Device Accountability form, and the serial number of the device used in a given session will be tracked in the subject's case file.

In accordance with Mayo Clinic policy, the brand, model, date of implantation, and date of explantation of all ES electrode leads will be recorded in the Surgical Inventory Management System. This information will be made available within the electronic medical record of each subject. Additionally, a copy of this information will be stored within each subject's case file.

5.8.4 Return or Destruction of Study Device

At routine intervals and at the completion of the study, there will be a reconciliation of devices shipped, devices utilized, and devices remaining. This reconciliation will be logged on the Device Accountability form, signed and dated. Any discrepancies noted will be documented, the PI will be notified, and an investigation will be conducted to determine the cause of the discrepancy.

6 STUDY PROCEDURES

6.1 Screening:

Subjects will complete a variety of assessments and procedures to determine their enrollment eligibility. When possible, eligible subjects will have their screening data used as baseline data collection. Primary outcomes include biomechanical assessments related to motor tasks, electrophysiology tests, and an ASIA examination. Secondary outcomes include spasticity assessments, subjective surveys, and various spine imaging.

6.2 Intervention 1: Transcutaneous Electrical Spinal Stimulation (TS) and Task Specific Training Sessions

Subjects will report to the ART lab at St. Mary's Hospital for daily sessions of TS and task-specific training interventions. TS stimulation will be applied to the skin surface over the spine as described previously.

Training sessions will begin upon completion of baseline testing. Subjects will participate in a 3 days per week training regimen over 1 month with a goal of achieving 12 sessions. Activities include tasks specific to supine intentional leg movement training, balance training, stand and step (reciprocal flexion/extension) training. Heart rate will be recorded prior to, and after, each session, and at any time the intervention is paused due to a concern. Environments include the body weight support treadmill (BWST) system to allow trainer-assisted stand and step activities as needed, custom standing frame, and a hi/lo mat for supine

and seated activities. As the subjects progress their intentional motor ability with standing and stepping, BWS will be removed, and assist will continue to be provided on an as needed basis. Any visit to the laboratory when TS is enabled will be considered a training session. Activities chosen for each session will be based on the subject's progression.

6.3 Period of Follow-up after TS

After 1 month of TS and motor training, each subject will be asked to complete two follow-up assessments at time points 1 month and 4 months after completing the intervention to monitor changes in primary and secondary outcome measures. Subjects will be asked to refrain from partaking in additional therapies or interventions with the goal of improving functional measures related to their SCI during this 4-month follow-up period.

6.4 Intervention 2: Epidural Electrical Stimulation (ES)

ES rehabilitation daily sessions will consist of lower extremity stretching, supine and side lying activities, seated trunk strengthening and balance activities, and locomotor training including task-specific stand and step training on a treadmill and over ground. Standing and stepping training activities may be performed with body weight support and trainer assistance as needed to ensure the safety of subjects.

Training sessions will begin upon completion of baseline testing. Subjects will participate in 3 days a week training regimen over 1 month with a goal of achieving 12 sessions. Activities include tasks specific to supine intentional leg movement training, balance training, stand and step (reciprocal flexion/extension) training. Heart rate will be recorded prior to, and after, each session, and at any time the intervention is paused due to a concern. Environments include the body weight support treadmill (BWST) system to allow trainer-assisted stand and step activities as needed, custom standing frame, and a hi/lo mat for supine and seated activities. As the subjects progress their intentional motor ability with standing and stepping, BWS will be removed, and assist will continue to be provided on an as needed basis. Any visit to the laboratory when ES is enabled will be considered a training session. Activities chosen for each session will be based on the subject's progression.

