1.4.2 Anticipated Risks

Risks associated with rehabilitation:

In combination with TS and ES, the rehabilitation techniques used during this study will focus on maximizing independence, load bearing, body position, and kinematics during motor tasks while providing the minimum amount of trainer assistance and body weight support necessary to safely perform tasks. Risks associated with daily training include skin irritation and minor bruising from pressure applied during trainer assistance and body weight support, musculoskeletal discomfort, fatigue, and bladder or bowel incontinence due to

exertion and abdominal pressure from support harness. There is a slight risk of fracture in the lower extremities. Orthostatic hypotension is a risk associated with abrupt position changes against gravity, specifically transitioning from sit to stand quickly.

Risks associated with weight-bearing tasks:

Risks include muscle soreness, fatigue, skin irritation, fracture, changes in blood pressure, and potential for a fall.

Risks associated with TS:

Skin irritation due to electrical current passing through human tissue, skin irritation due to adhesives used to apply skin surface electrodes, discomfort or abdominal tightness during TS, increased or decreased spasticity, bowel or bladder incontinence, shortness of breath, muscle soreness, or fatigue may occur. Autonomic dysreflexia is a risk for those with midthoracic or higher-level injuries. Skin irritation or burns may occur during high-amplitude stimulation and/or prolonged stimulation sessions; skin breakdown may also occur as a result of this stimulation, with ensuing infection being a potential risk.

Risks associated with temporary percutaneous implantation of ES electrode leads:

ES electrodes will be implanted via commonly used percutaneous implantation techniques for FDA-approved treatment of medically refractory pain conditions. Therefore, the risks associated with percutaneous implantation of the ES system for this study match the risks associated with ES system implantation for treatment of FDA-approved conditions.

- Undesirable changes in stimulation may occur over time. These changes in stimulation are possibly related to cellular changes in tissue around the electrodes, changes in the electrode position, loose electrical connections and/or lead failure.

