3 STUDY DESIGN

3.1 General Design

This is a pilot study that will include a total of 8 subjects with chronic, motor complete or incomplete paralysis below the level of SCI. All subjects will complete either 1 month of TS or ES driven physical rehabilitation sessions (**Table 1**). All subjects will then be followed for an additional 4 months for follow-up assessments. Expected duration of subject participation is less than 6 months.

Table 1: Study Design

	PRE-INTERVENTION	INTERVENTION	POST-INTERVENTION	Follow-Up					
Subjects	Baseline Assessments	Minimum 12 Sessions	ents	Assessments					
50% of Sub	Clinical, Electrophysiology, Kinematic Assessments & Surveys	Stimulation + Motor Training	Training Kinematic Assessments						
	Tr	Kinematic	Kinematic veys	END					
	DDE INTERVENTION					∠			
	PRE-INTERVENTION	INTERVENTION	POST-INTERVENTION	Sul	ogy, Sur				
jects	Baseline Assessments	Minimum 12 Sessions		nysiology, & Sul	nysiology, & Sur	STUDY			
50% of Subjects		Minimum 12 Sessions Stimulation + Motor		Electrophysiolc &	Electrophysiolo &	STUD			
₽	Baseline Assessments Clinical, Electrophysiology, Kinematic Assessments & Surveys	Minimum 12 Sessions Stimulation + Motor	End Assessments Clinical, Electrophysiology, Kinematic Assessments & Surveys	Clinical, Electrophysiology, & Su	Clinical, Electrophysiology, & Sur	STUD			

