retested after two weeks' time for resolution. The subject will also be screened during a mock-up therapy session utilizing body weight supported harness system over the treadmill and trainer assistance to facilitate stand and step activities while monitoring blood pressure, tolerance, and range of motion. Due to an absence of standardized clinical practice guidelines that inform rehabilitation task safety decisions, if any concerns related to upright and load bearing activities exists, i.e. limited range of motion of load bearing joints, high spasticity, low blood pressure, osteoporosis (defined as a DEXA t-score of -3.5 or lower at the spine and hip), or high body weight, participants will receive motor training while seated and/or supine on a mat table, to avoid injury related to load-bearing activities. Based on screening results, a final decision on study participation will be made by the PI and study team. If any exclusionary screening results are transitory in nature, the subject may be re-screened at the discretion of the investigators. Screening tests will be repeated as indicated in the Study Procedures section.

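### Does the longer activity list in section 6.4 mean that the ES arm is trained differently from the TS arm?

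*Combined protocol and SAP*

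**What the plan says.** Section 6.4 begins with a paragraph on content: "ES rehabilitation daily sessions will consist of lower extremity stretching, supine and side lying activities, seated trunk strengthening and balance activities, and locomotor training". It places the locomotor part as "task-specific stand and step training on a treadmill and over ground". Section 6.2 has no equivalent opening; it refers only in general terms to TS with task-specific training.

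Both sections then carry nearly the same paragraph: three days a week for one month, a goal of 12 sessions, and the same list, "Activities include tasks specific to supine intentional leg movement training, balance training, stand and step (reciprocal flexion/extension) training". The environments are also the same: a body-weight-support treadmill, and "custom standing frame, and a hi/lo mat for supine" and seated work. Both end by letting the activities of each session follow the subject's progress.

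Section 6.2 defines a session broadly: "Any visit to the laboratory when TS is enabled will be considered a training session". Section 6.4 has the same rule for ES.

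For any subject with a load-bearing concern, section 4.3 says that "participants will receive motor training while seated and/or supine on a mat table, to avoid injury related to load-bearing activities". The risk section treats the training of the two arms together: "In combination with TS and ES, the rehabilitation techniques used during this study will focus on maximizing independence, load bearing, body position".

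The items tied to each session are heart rate (6.2 and 6.4) and the serial number of the TS device (5.8.3). Photographs and video are taken during the study (6.6). Section 10.3 makes the case report form the main data collection instrument but does not list its fields.

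**The concern.** Section 2 sets out to compare TS and ES, each combined with rehabilitation. Read literally, 6.4 gives ES subjects stretching, side-lying and over-ground work that 6.2 does not give TS subjects. Those items lie close to what is measured. Side-lying is one of the biomechanical assessment tasks. The modified functional reach test measures trunk stability. The Timed Up and Go, Berg and 6 Minute Walk tests assess mobility and balance in subjects with motor-incomplete injury.

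An ES advantage on such measures could then come from practice rather than from the route of stimulation. The number of sessions would not reveal this, because any stimulation-enabled visit counts as one. Without a log of activities, nobody could later say what each subject had received. The same gap would trouble the hope, stated in the Introduction, of telling responders from non-responders: a poor response could simply reflect less, or different, training.

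**Working it through.** The plan gives no figure to reproduce, and no power formula applies (8.1 states that no power calculation was done). The check is a comparison of text.

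**1. Opening list of 6.4 against 6.2, with stand/step counted once**

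| Activity in 6.4 | In 6.2? |
|---|---|
| Supine | Named |
| Balance | Named |
| Stand/step | Named |
| Seated trunk strengthening | Partly (balance training; mat for seated work) |
| Stretching | No match |
| Side-lying | No match |

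3 named + 1 partly covered + 2 unmatched = 6. Of the two stand/step settings in 6.4 (treadmill, over ground), one, over ground, is not named in 6.2. Nothing is named for TS alone.

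**2. Does 6.2 exclude the unmatched items?** No. Its list and its environments are both introduced as inclusions, so they are open. It also says that body-weight support comes off as standing and stepping improve, which leaves room for over-ground work.

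**3. Does 6.4 fix a package for ES?** No. Its second paragraph repeats the 6.2 list and ends with the same rule that each session follows the subject's progress. The opening list therefore cannot be a set programme given in full every time.

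**4. What do other sections say?** Section 1.4.2 describes one set of techniques for both arms. Table 1 gives both halves of the sample stimulation plus motor training. Table 3 has a single motor-training row. Section 2.2 refers to 12 sessions with either form of stimulation. None separates training by arm.

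**5. How far could a difference reach?** One subject per impairment grade per intervention (1.1) gives 4 per arm. The modified functional reach test could involve up to 4 v 4. Under the motor-incomplete rule (grades C and D), the mobility tests involve 2 v 2. At 3 sessions a week for 4 weeks, each subject has 12 sessions, and 8 × 12 = 96 in all if each completes exactly 12. (Table 1 puts "Minimum 12 Sessions" where 6.2 and 6.4 set a goal of 12; that wording needs reconciling but is a separate matter.)

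**6. Is a record missing?** Only its description is. The case report form is not in the documents. Section 10.2 lists laboratory notes and evaluation checklists among examples of source documents, and 5.4 and 11.1 provide for review of all protocol procedures and records. This does not prove that an activity log exists; equally, nothing shows that one is absent.

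**The case for a change.** The best case for a change is that it is cheap and that lost information may be hard to recover. A shared paragraph would settle the wording. A short entry per session would cost 96 × 3 min = 288 min = 4.8 hours to 96 × 5 min = 480 min = 8.0 hours, on an assumed 3 to 5 minutes each. Impairment grade is balanced across arms by design, and training content is another factor within the sponsor's control. With so few subjects, interpretation rests on individual descriptions, and knowing what each did would help in reading them.

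Part of this stands. The two sections are uneven, a reader cannot be certain whether that was meant, and a listing of training by subject would be useful. But its use is descriptive. Activities vary with progress and with the safety rule in 4.3 even if the two sections were worded identically. Arms are assigned by availability or by the subject's choice (5.2), and one subject per grade per arm cannot support adjustment for training. The cost figure covers writing the entry only. Timing each activity during a session would add work, and the documents give no figure for it.

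**Conclusion.** The difference in wording is real and small: two of six activities, and one of two stand/step settings, are named for ES and not for TS. It does not establish a difference in training, because the TS list is open, the operative paragraph is nearly the same in both sections, and the rest of the protocol describes training jointly. Uneven drafting is the natural reading, and trial staff can apply the shared text sensibly.

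No stated rule has been shown to give a wrong result, and no conclusion has been shown to depend on the difference. The size and direction of any bias cannot be derived from the documents; session length, for instance, is not given. This is a pilot with 4 v 4 subjects, non-randomised, without a power calculation, and 3.2 says that designating primary endpoints is not feasible. Section 2 already takes stimulation together with rehabilitation as the unit of comparison.

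The judgment rests on reading 6.2 as open and on not treating an unseen case report form as deficient. A statement by the sponsor that training content differs by arm would reopen the question. Bringing the two sections into line is an editorial matter, and I take no position on which activities belong in either arm. Confirming that session notes capture the activities performed is an optional check. Neither is a change that the statistical plan requires.
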